10.0 Privacy/Confidentiality Issues

All study protocols and procedures will be submitted to the site's Institutional Review Board for approval. All data collected will be stored in a secure REDCAP database, accessible only by key study personnel. The following identifying information will be collected: age, medical record number, admission date, and discharge date. Patient-reported congestion score surveys will be de-identified, using a study identification number. All patient-reported congestion score surveys and consent forms and will be stored in a locked cabinet in the site investigator's office. For statistical analyses, all identifying information will be removed. Candidates aged > 89 years will be condensed into a category of age greater than or equal to 90 years of age to protect their identity.

Appendix A: Schedule of Study Assessments

	Screen	Baseline	12 hrs	24hrs	36 hrs	48 hrs	Day 30 (Phone Call)
Informed Consent	x						
Inclusion/Exclusion Criteria	x						
Screening electrolytes, renal function, liver function, pregnancy status if applicable	x						
Vital Signs	x	x	x	x	x	x	
Standing Weight		x		x		x	
Current Cardiovascular Medications		x		x		x	
Loop diuretic regimen evaluation	x	x		x		x	
BMP	x	x	x	x	x	x	
Biobank blood		x		x		x	
Biobank plasma		x		x		x	
Urine Collection	x	x	x	x	x	x	
Congestion Score Assessment		x		x		x	
Adverse Event Assessment				x		x	
Outcomes Assessment						x	x

Appendix B: Patient-Reported Congestion Score

This score will be done at enrollment and repeated at 24 and 48 hours.

To be completed by patient. "Please draw a horizontal line on the scale to show how you think your fluid or congestion is right now. The number "0" equals the worst your fluid or congestion has ever felt and the number "10" equals the best your fluid or congestion has ever felt."

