5.4 Study Outcomes

The primary outcome will be 48-hour standing scale weight change (kg) from enrollment among the metolazone, intravenous chlorothiazide, and tolvaptan arms, using metolazone group as the comparator group for all other groups.

Secondary outcomes, using metolazone as the comparator group for each, will be:

- 48 hour net urine output (mls)
- mean change in serum creatinine, blood urea nitrogen, and eGFR at 24 hours, 48hours, and at hospital discharge
- mean change in diuretic efficiency at 24 and 48 hours from baseline value at enrollment
- mean change in serum potassium at 24 and 48 hours from baseline value at enrollment
- mean change in serum sodium at 24 hours, 48hrs, and at discharge from baseline value at enrollment
- cumulative dose of potassium (mEq) and magnesium (g) supplementation administered at 24 and 48 hours
- incidence of severe hypokalemia
- need for escalation in study-directed loop diuretic therapy at 24 and 48 hours
- addition of vasoactive or inotropic medication at 24 and 48 hours
- Treatment failure (definition below)
- Patient-scored congestion visual analog scale score at baseline, 24 and 48 hours (Appendix B)
- new cardiac arrhythmias (atrial and ventricular) during the study period
- receipt of inotropic therapy, dopamine, or nitroglycerin; requirement of ultrafiltration or hemodialysis during index hospitalization
- in-hospital mortality
- pharmacoeconomic analysis of the direct costs in each arm including the cost of:
 - study medication
 - additional non-trial protocol laboratory analysis cost related to monitoring of electrolytes
 - treatment of study medication related adverse effects (arrhythmias, hypotension, electrolyte repletion)
 - escalation of loop diuretic therapy doses
 - addition of additional therapies for suboptimal diuresis (inotropic therapy, vasodilators)
 - new initiation of renal replacement therapies (hemodialysis or ultrafiltration)
- Spot urinary electrolytes and diuretic urine concentration
- Pharmacokinetics and pharmacodynamics of the diuretics in the urine and blood
- Fractional excretion of sodium

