5.6 Study Outcome Timeline

Day 1: Baseline standing weight, BMP every 12 hours, urine collection, 20ml blood collection dyspnea score.

Day 2: 24 hour urine collection/quantification, BMP every 12 hours, 24 hour standing weight, 20ml blood collection, 24 hour dyspnea score, receipt of non-study diuretics, need of new inotropes or vasodilators

Day 3: 48 urine collection/quantification, 48 hour standing weight, 20ml blood collection, 48 hour dyspnea score, receipt of non-study diuretics, need of new inotropes or vasodilators.

End of study.

Day 30 (+/- 2 days): Telephone contact for the following events in past 30 days:

- ER visits and reason for visits
- Hospitalizations and reason for hospitalizations
- Serious adverse events

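### Section 5.6 calls the patient-reported congestion score a dyspnea score, and the plan names no analysis that uses its baseline value

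*Combined protocol and SAP*

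**What the plan says.** **Name of the measure.** Section 5.4 lists the secondary outcome as "Patient-scored congestion visual analog scale score at baseline, 24 and 48 hours (Appendix B"). Appendix A has a row headed "Congestion Score Assessment", marked at baseline, 24 and 48 hours, and no row for dyspnea. Appendix B supplies the scale and its timing: "This score will be done at enrollment and repeated at 24 and 48 hours". Section 10.0 refers to the completed forms as congestion score surveys. Section 5.6 differs. Its Day 1 entry reads "Baseline standing weight, BMP every 12 hours, urine collection, 20ml blood collection dyspnea score", Day 2 has "24 hour dyspnea score" and Day 3 has "48 hour dyspnea score". It does not mention a congestion score.

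**Scale.** Appendix B ties both ends to the patient's own history: 0 is the worst that patient has ever felt, and 10 "equals the best your fluid or congestion has ever felt".

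**Analysis.** In Section 5.4, creatinine, blood urea nitrogen, eGFR, diuretic efficiency, potassium and sodium are defined as mean changes. The congestion item is defined as the score at each of three times. Section 9.3 assigns a Student's t test against metolazone to continuous secondary outcomes and mentions no covariate. Section 9.1 gives 60 patients in three equal arms, so 20 per arm.

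**The concern.** Two things are unsettled for the only patient-reported scale among the listed outcomes.

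First, the document uses two symptom names for what appears to be one measure. Dyspnea and congestion are different constructs. Under Section 3.0 a patient without catheterization data can qualify on edema and ascites, and such a patient may have little breathlessness. A reader of the results should be able to tell which symptom was prespecified.

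Second, a baseline score is collected but no stated analysis uses it. Patients rate themselves against personal extremes, so part of the spread in follow-up scores reflects where each patient places those extremes and how congested each was at entry. Leaving that spread in the error term weakens a comparison of 20 against 20. It also leaves the result exposed to chance imbalance at baseline.

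**Working it through.** **Name.** Four places (Sections 5.4 and 10.0, Appendices A and B) say congestion; one (Section 5.6) says dyspnea, on three days. The Section 5.6 times (Day 1, 24 hours, 48 hours) coincide with those in Section 5.4 and both appendices. The only instrument supplied is the congestion scale. The simplest reading is one instrument with a wrong label in Section 5.6, although the text does not say so.

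**Inputs for the baseline question.** 20 per arm (Section 9.1); two-sided 0.05 (Section 9.3). The documents give no standard deviation (SD) and no baseline-to-follow-up correlation r for this score. Results are therefore in SD units, r is assumed, and the SD is taken as equal at baseline and follow-up.

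**The plan's own figure.** Section 9.2 states 82.3% power for the primary weight outcome. A two-sample t test with 20 per arm and a standardized difference of 1.5/1.6 = 0.94 gives 82.4%. That figure reproduces and is not in dispute. The plan states no figure for the congestion score.

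**Variance of the arm difference relative to the raw follow-up score**

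- Raw follow-up score: 1
- Unadjusted change from baseline: 2(1 − r)
- ANCOVA on the baseline score: 1 − r²

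| Assumed r | Change score | ANCOVA | Reduction with ANCOVA | Equivalent patients per arm |
|---|---|---|---|---|
| 0.3 | 1.40 | 0.91 | 9% | 20/0.91 = 22 |
| 0.5 | 1.00 | 0.75 | 25% | 20/0.75 = 27 |
| 0.7 | 0.60 | 0.51 | 49% | 20/0.51 = 39 |

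**Detectable difference at 80% power.** Raw score: 0.91 SD. ANCOVA: 0.91 × √(1 − r²) = 0.87, 0.79 and 0.65 SD at r = 0.3, 0.5 and 0.7. Unadjusted change: 0.91 × √(2(1 − r)) = 1.08, 0.91 and 0.70 SD.

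**Power for a true difference of 0.8 SD.** Raw score: 69%. ANCOVA: 73%, 81% and 93%. Unadjusted change: 55%, 69% and 89%. A plain change score is thus worse than the raw score when r is below 0.5, while ANCOVA is better at every r shown.

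**Chance imbalance.** The standard error of a baseline difference between two arms is √(2/20) = 0.32 SD, a 95% range of about ±0.62 SD. An unadjusted comparison of follow-up scores carries that imbalance forward in proportion to r.

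**Equivalence.** Regressing the change on arm and baseline gives the same treatment estimate and standard error as regressing the follow-up score on arm and baseline. Only the baseline coefficient shifts, by 1. Either form can be written into the plan.

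**The case against.** The case for leaving this alone has several parts.

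- *The dyspnea wording does no practical harm.* This largely stands. The trial has a single center (Section 4.0), the times match, and staff have no dyspnea form to administer. A reader might infer that the wrong symptom will be collected and the listed one missed; the documents do not support that. The contradiction still needs correcting.
- *The plan does not say that baseline will be ignored.* This stands. A reader might infer a commitment to compare raw scores without regard to baseline, or to test the arms against each other at baseline. Neither is stated: Section 5.4 gives the times at which the score is taken, and a t test could be run on changes. What can be said is that no analysis using the baseline is named.
- *Randomization already protects the comparison.* It does protect against bias on average. It does not recover the lost precision.
- *The variance gain is generic and rests on an assumed r.* Also true. It would apply to any continuous outcome with a baseline value, and at r = 0.3 it is modest. It is not evidence that self-anchoring does damage.
- *Adjustment does not cure self-anchoring.* Correct. With personal anchors at both ends, the size of a one-point step also differs between patients. Adjustment can reduce differences in level but cannot make the units common.
- *The direction of the scale is unclear.* A reader might infer this because a higher congestion score means less congestion. But Appendix B states both anchors and Section 5.4 cites Appendix B, so there is no defect here.

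**Conclusion.** The point holds in a limited form. Section 5.6 contradicts four other places on the name of the patient-reported measure. This is a labelling error with little risk that the wrong thing is collected. The analysis of the score is also under-specified: the plan names no method that uses a baseline value it already collects.

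The cost is precision on one secondary outcome. For assumed correlations of 0.3, 0.5 and 0.7, about 9%, 25% and 49% of the variance of each comparison with metolazone could be removed. These figures assume equal SDs at baseline and follow-up and a linear relation between the two, and they ignore the one degree of freedom spent on the covariate. The primary outcome, its power and the sample size are unaffected.

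**What to change.** 1. In Section 5.6, replace the dyspnea score on Days 1, 2 and 3 with *Patient-Reported Congestion Score (Appendix B)*.
2. In Section 5.4, restate the outcome as the Appendix B score at 24 and at 48 hours, adjusted for the baseline score. Change from baseline with the same adjustment is equivalent.
3. In Section 9.3, add one sentence: the 24- and 48-hour congestion scores in the chlorothiazide and tolvaptan arms are each compared with metolazone by ANCOVA with the baseline score as covariate, and baseline scores are described by arm but not tested. Avoid an unadjusted change score, which loses precision if the correlation is below 0.5.

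The cost is wording in three sections. The baseline score is already scheduled, so there is no added visit, form or burden for patients.

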Appendix C: 30-Day Follow up Telephone Call Script

The site investigator will perform this phone call at 30 ± 2 days after enrollment.

Hello, my name is Dr. (name) from (Medical Center). I am calling to briefly follow up with you about the research study you participated in during your recent hospitalization for heart failure approximately one month ago. The study compared 3 different types of fluid removal medications in combination with furosemide (Lasix) and was called “Comparison of oral thiazides versus intravenous thiazides versus tolvaptan in combination with loop diuretics for diuretic resistant decompensated heart failure”.

Do you have time now to complete the brief post-study survey that was mentioned to you at the start of the study? It should take no more than 5 minutes of your time. Thank you for your participation.

If subject has deceased since discharge

I am very sorry for your loss. It is important that we ask 3 simple questions to understand this unfortunate event. Could you please tell me:

- Date of death
- Cause of death
- Location of death
 - Out-of-hospital
 - In-hospital
 - Initial reason for hospitalization

If subject is alive

Since your discharge from (Medical Center) on (Discharge Date), have you experienced any of the following events?

1. Admission to any hospital?
 - a. Admission reason:
 - i. Heart failure
 - ii. Heart rhythm issue
 - iii. Low blood pressure
 - iv. Heart attack
 - v. Cardiac arrest
 - vi. Kidney failure
 1. Was dialysis required?
 - vii. Other (free text)
2. Gone to any emergency room?
 - a. Reason for emergency room visit:
 - i. Heart failure
 - ii. Heart rhythm issue

- iii. Low blood pressure
- iv. Heart attack
- v. Cardiac arrest
- vi. Kidney failure
- vii. Other (free text)

- 3. Any other serious health event?
 - a. Document event if so

This ends your participation in this research study. Thank you very much for your participation in this research study and for your time today. Your participation is helping our medical team understand how to treat patients with heart failure better. Do you have any other questions at this time?

Goodbye.

End of Script

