7.2 Reporting of SAE

All serious adverse events occurring from randomization through the 30 day follow-up period will be collected. The Site Investigator is responsible for monitoring the safety of patients enrolled into the study. The following adverse events are anticipated, disease related-events in patients with decompensated heart failure however they should still be reported on the Serious Adverse Event form in the REDCAP Database (some may require reporting as study endpoints):

- New Atrial Arrhythmia: A “new” diagnosis of atrial arrhythmia (includes atrial fibrillation, atrial flutter, ectopic atrial tachycardia) lasting > 30 seconds OR any atrial arrhythmia which causes hemodynamic instability (MAP < 60 and requiring intervention)
- New Ventricular Arrhythmia: Ventricular tachycardia lasting longer than 30 seconds, or frequent non-sustained VT causing hemodynamic instability with MAP < 60 mmHg requiring intervention or > 1 intra-cardiac defibrillation or external cardiac defibrillation shock or ventricular fibrillation requiring defibrillation
- Hypotension: SBP < 85 for 2 repeated measurements within 30 minutes or lasting at least 30 minutes or symptomatic hypotension necessitating clinical intervention (defined as vasopressor support, intravenous fluid boluses, or initiation of inotropes)
- Myocardial infarction: a cardiac event including an elevation in troponin above baseline with or without ECG changes that is judged to be a myocardial infarction by the treating attending cardiologist
- Cardiac arrest: any ventricular arrhythmic or pulseless electrical event that requires immediate life-sustaining medical therapies
- Acute renal failure: A rise in serum creatinine of 1 mg/dl or more from the baseline serum creatinine in the 48 hour treatment period
- Acute renal failure requiring dialysis: an acute renal failure event that began during the 48 hour study period and necessitates new hemodialysis during the hospitalization

- Worsening heart failure: the need for rescue therapy (additional open label loop diuretic, spironolactone doses >75mg/day, eplerenone > 75mg/day, non-study thiazides (at a dose of metolazone 2.5mg or greater equivalence), systemic acetazolamide (for diuretic indication), triamterene, amiloride, ultrafiltration, hemodialysis, or mechanical circulatory or respiratory support) in the 48 hour treatment period
- Death
- Metabolic SAE (during 48 hour treatment period):
 - Severe Hypokalemia: Serum potassium value < 3.0mEq/L

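### The Day 30 script asks about earlier admissions, ER visits and other serious events only if the patient is alive, so non-fatal events before a post-discharge death may be missed

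*Combined protocol and SAP*

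**What the plan says.** Section 5.6 describes the Day 30 contact as "Telephone contact for the following events in past 30 days", and lists ER visits and hospitalizations, each with its reason, and serious adverse events. Section 7.2 states: "All serious adverse events occurring from randomization through the 30 day follow-up period will be collected". Section 8.0 says that patients withdrawn after overcorrection of sodium are also followed to Day 30.

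Appendix C is the instrument for this contact: "The site investigator will perform this phone call at 30 ± 2 days after enrollment". It has two branches.

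- The first, headed "If subject has deceased since discharge", tells the caller: "It is important that we ask 3 simple questions to understand this unfortunate event". The items are date, cause and location of death. Under an in-hospital location there is one further item, "Initial reason for hospitalization".
- The second, for living patients, opens with "Since your discharge from (Medical Center) on (Discharge Date), have you experienced any of the following events". It asks about hospital admissions with reasons, ER visits with reasons, and any other serious health event, where the instruction is "Document event if so". None of these three questions has a prompt for a date.

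Appendix A schedules adverse event assessment at 24 and 48 hours. After 48 hours the only scheduled column is the Day 30 call, marked for outcomes assessment.

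**The concern.** The instrument does not collect what Sections 5.6 and 7.2 call for in one identifiable group: patients who die between discharge and the call. A caller who follows the script learns how, when and where the patient died, but not whether there was an earlier readmission, ER visit or serious event. Whether non-fatal events are asked about therefore depends on death, which is itself an outcome. If deaths are unevenly spread over the arms, the non-fatal 30-day counts will be incomplete to different degrees.

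The missing date prompts are a second, smaller gap. Section 7.1 requires a causality judgement for any SAE, and timing relative to study drug is part of that judgement. As scripted, an event soon after discharge and one four weeks later would be noted in the same way. Unexpected SAEs also count toward the five-event halt in Sections 7.2 and 7.3, so incomplete capture bears on that safeguard too.

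**Working it through.** The plan states no figure on this point, so the main check is a comparison of the requirement with the script.

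| Item | Required by | Living-patient branch | Deceased branch |
|---|---|---|---|
| Hospitalizations and reasons | 5.6 | Asked, undated | Only the reason for admission when death was in hospital |
| ER visits and reasons | 5.6 | Asked, undated | Not asked |
| Other serious events | 5.6, 7.2 | Asked, undated | Not asked |
| Death | 7.2 | Not applicable | Date, cause, location |

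**Is there another route?** Section 7.2 has SAEs entered in a separate REDCap record, but that record can hold only what the site learns. After 48 hours Appendix A schedules no contact except the call, and no section describes a chart review or retrieval of outside records. In addition, the SAE criteria in Section 7.0 list prolonged hospitalization but not a new admission. A readmission or ER visit is therefore not automatically an SAE, and for many such events the call is the only source described. The stretch from 48 hours to discharge is outside the look-back of both branches and has to come from the index hospital record.

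**Which outcomes are touched?** The outcomes in Section 5.4 are tied to 48 hours, discharge or the index hospitalization. The cost outcome states no time horizon, but readmissions and ER visits are not among its components. Section 9.3 plans no 30-day comparison. What is left is the descriptive 30-day safety follow-up.

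**How much does one patient weigh?** Section 9.1 gives 60 patients in three equal groups, so 60 / 3 = 20 per arm. One patient with a missed event is 1 / 20 = 5 percentage points of that arm. This is a unit of scale, not a forecast.

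**How much doubt do the missing dates leave at Day 30?** Let C be the day of the call (28 to 32) and L the day of discharge. The look-back is C − L days, and the part beyond Day 30 is max(0, C − 30).

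- C = 28: 0 days beyond Day 30; Days 29 and 30 are not covered.
- C = 30: 0 days beyond, 0 days uncovered.
- C = 32: 2 days beyond. The documents give no discharge day, so I assume three values. L = 3: 2 / 29 = 7% of the look-back. L = 7: 2 / 25 = 8%. L = 14: 2 / 18 = 11%.

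For a call made in the window, the doubt about whether an event falls inside 30 days is at most 2 days, and arises only for calls on Day 31 or 32.

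**The case against.** The best defence is that the script is a spoken guide and not the case report form. SAEs have their own REDCap record, are followed to stabilization or resolution, and go to the sponsor within 24 hours of the investigator being notified. The REDCap fields are not in the documents, so a missing spoken prompt does not prove that dates go unrecorded. This stands in part: it rules out saying that the events are certain to be lost. It does not supply a route by which the site would learn of an outside admission or ER visit in a patient who later died.

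Three further points on this side stand.

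- A reader might infer that nothing about admissions is asked after a death. That is not so: the reason for a terminal admission is requested.
- A reader might infer that undated events cannot be placed within 30 days. For most they can, because the discharge date and the call date bound every reported event.
- A reader might infer that harm could pass for benefit in the trial's comparisons. No planned comparison uses these data. Deaths are recorded with date, cause and place, so an arm with more deaths would show them. Death also shortens time at risk, so raw non-fatal counts would fall somewhat even with complete questioning. The distortion is confined to descriptive 30-day counts.

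The ±2-day call window is stated consistently in Section 5.6 and Appendix C and applies to all arms. Moving it would be a preference, not the correction of an error.

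**Conclusion.** The point holds as a mismatch between the protocol and its own instrument. Followed as written, Appendix C leaves out earlier admissions, ER visits and non-fatal serious events in patients who die after discharge, although Sections 5.6 and 7.2 require them. They are at risk of being missed, not certain to be. The effect is on the completeness of the descriptive 30-day safety data; the primary outcome and the listed secondary outcomes are unaffected.

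The number of patients involved cannot be derived. The documents give neither a post-discharge death rate nor the share of such patients with an earlier event, and any count would rest on assumed values for both. The conclusion rests on two readings: that callers keep to the script, and that no record review takes place beyond what the documents describe. If the site routinely searches records for patients who have died, the gap is smaller, and the protocol should say so.

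**What to change.** In Appendix C:

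1. In the deceased branch, also put questions 1 to 3 (admissions, ER visits, other serious events) to the informant, for the period from discharge to death.
2. In both branches, record the date of each reported event, approximate if necessary, with a matching REDCap field if none exists. This gives the causality assessment in Section 7.1 the timing it needs, and allows events after Day 30 to be set aside when the call falls on Day 31 or 32.

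The call window can stay as it is. No analysis, sample size or treatment changes. The cost is a few script lines, possibly some date fields, and a slightly longer call with a bereaved informant, whose recall may be incomplete.

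### SAEs are promised through Day 30, but no scheduled procedure ascertains them between 48 hours and discharge, and the Day 30 script does not carry out the look-back in Section 5.6

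*Combined protocol and SAP*

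**What the plan says.** Section 7.2 sets the window: "All serious adverse events occurring from randomization through the 30 day follow-up period will be collected". It also makes the site investigator responsible for safety monitoring and requires SAEs to be recorded, followed until they settle, and notified to the sponsor within 24 hours of the investigator learning of them.

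Section 5.6 describes the follow-up call as "Day 30 (+/- 2 days): Telephone contact for the following events in past 30 days", and SAEs are on the list beneath it.

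Appendix A marks the row "Adverse Event Assessment" at 24 and 48 hours only. Day 30 carries a mark only in the row "Outcomes Assessment". There is no discharge column.

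The Appendix C script puts all its questions to a surviving patient, including the open item on other serious events, under the stem "Since your discharge from (Medical Center) on (Discharge Date), have you experienced any of the following events". The branch for a patient who has died is also limited to the time after discharge.

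Section 5.4 carries some outcomes beyond 48 hours: in-hospital death, ultrafiltration or hemodialysis during the index stay, and creatinine, BUN, eGFR and sodium at discharge.

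**The concern.** Two sections state a window that includes the hospital days after treatment, but neither instrument used to fill that window reaches those days. Site staff work from the schedule and the script. If they follow both as written, they look for adverse events at 24 and 48 hours and then ask about the time after the patient has gone home. New SAEs that begin after 48 hours and before discharge depend on someone noticing and reporting them unprompted.

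At stake is the completeness of the safety data in a trial whose second aim concerns electrolyte and renal harms. With 20 patients per arm, a few unrecorded events would be a noticeable share of the total. The rule that pauses the trial after 5 unexpected SAEs (Sections 7.2 and 7.3) also depends on events being found promptly.

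**Working it through.** The plan's main design figure is the 82.3% power in Section 9.2. It reproduces: a two-sample t test with 20 per arm, a difference of 1.5 kg, an SD of 1.6 kg and two-sided alpha of 0.05 gives 82.4%. No SAE quantity enters it, so it has no bearing on this point. The check is a comparison of windows.

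| Place | Time covered | What it captures |
|---|---|---|
| 7.2 | Randomization to Day 30 | All SAEs (the commitment) |
| 5.6 | 30 days before the call | Emergency visits, admissions, SAEs |
| Appendix A, adverse event row | 24 h and 48 h | Adverse events |
| Appendix A, outcomes row | 48 h and Day 30 | Outcomes, content not itemized |
| Appendix C, surviving patient | Discharge to call | Admissions, emergency visits, other serious events |
| 5.4, index-stay items | To discharge | Death, dialysis or ultrafiltration, discharge creatinine, BUN, eGFR, sodium |
| 5.4, potassium change | 24 h and 48 h | Serum potassium |
| 5.4, new arrhythmias | Study period, which Section 4.0 sets at 48 h from first dose | Atrial and ventricular arrhythmia |

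1. **0 to 48 hours:** covered by the adverse event row.
2. **Discharge to Day 30:** covered by the script.
3. **48 hours to discharge:** covered by neither. Only the 5.4 index-stay items reach it. They pick up death and renal support, plus single laboratory values at discharge, which can miss a creatinine or sodium excursion that has recovered by then. Potassium change and new arrhythmias stop at 48 hours.
4. **The 5.6 look-back:** this would reach interval 3 if applied, but the script replaces it with a shorter one. Even the full look-back relies on a patient recalling inpatient events by telephone, which suits laboratory-based events poorly.

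**Length of interval 3.** The documents give no length of stay, so discharge day L after first dose is an assumption. Gap = L − 2 days; share = (L − 2)/30.

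| L (days) | Gap (days) | Share of 30 days |
|---|---|---|
| 3 | 1 | 3% |
| 5 | 3 | 10% |
| 7 | 5 | 17% |
| 10 | 8 | 27% |
| 14 | 12 | 40% |

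These are shares of calendar time, not of events. The documents give no basis for estimating how many SAEs would fall in the interval.

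**The case against.** The strongest reply is that SAE reporting is a standing duty, not tied to visits. Section 7.2 obliges the investigator to collect all SAEs to Day 30, at a single center where the patient is still an inpatient. Section 5.6 already states the right look-back. Appendix A is also not exhaustive: the discharge laboratory values required by 5.4 have no column there either, so a missing column does not prove that nothing is collected.

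Much of this stands. It rules out saying that the interval is uncovered or that its events would be lost. An SAE already recorded by 48 hours would be followed to resolution. What the reply does not supply is a procedure for finding new events: no section names one for this interval, and the script contradicts the section that could have served.

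Three stronger inferences are tempting, and the documents support none of them:

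- **Late events fall outside the SAE definition.** The general definition in Section 7.0 has no 48-hour limit. Section 7.2 limits some listed entries to the treatment period (metabolic events, acute renal failure, worsening heart failure) and counts dialysis for "an acute renal failure event that began during the 48 hour study period and necessitates new hemodialysis during the hospitalization". The entries for arrhythmia, hypotension, myocardial infarction, cardiac arrest and death have no such limit. A late event that meets the general definition must still be collected.
- **A 30-day SAE comparison between arms would be biased.** Neither 5.4 nor 9.3 plans one.
- **The 48-hour windows close 12 hours after the last active dose in every arm.** Section 5.2 gives the thiazides every 12 hours but active tolvaptan once daily, so one figure cannot describe all arms.

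**Conclusion.** The point holds as an inconsistency between the commitment and the instruments. Sections 7.2 and 5.6 promise SAE ascertainment over 30 days; Appendix A and Appendix C, followed literally, schedule none from 48 hours to discharge. Coverage of that interval is partial, through general reporting and the 5.4 index-stay outcomes. Under-ascertainment is most plausible for non-fatal SAEs that do not lead to renal support, such as arrhythmia or hypokalemia meeting the SAE definition.

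The interval is 1 to 12 days on the assumed range of stays, and the number of events at risk is unknown. The textual conflict itself rests on no assumption. The consequence is confined to the completeness and timeliness of safety data; the 48-hour weight outcome, its analysis and the power do not change. It is worth correcting because the remedy is small.

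**What to change.** 1. **Appendix C:** change the stem for surviving patients to cover the time since enrollment, in line with 5.6. Anchoring on enrollment also avoids drift with the ±2-day call window: a 30-day look-back from a call on day 32 would start on day 2 (32 − 30).
2. **Appendix A:** add a discharge column with an SAE chart review from 48 hours to discharge, done together with the discharge creatinine, BUN, eGFR and sodium abstraction that 5.4 already requires.
3. **Appendix A:** add an SAE mark at Day 30, so that the schedule agrees with 5.6 and 7.2.

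The 48-hour windows on individual entries in 7.2 can stay as they are; an additional reporting window for metabolic events would be a preference, not a correction.

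The cost is one short chart review for each of the 60 patients and a wording change. No new tests or visits are needed. The downside is that more events will be found and will have to be reported.
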